## 7. REPORTING CONVENTIONS

### 7.1 General reporting conventions

All tables, figures and data listings will be presented in portrait orientation, unless landscape orientation suggests that the information is easier to view. Legends will be used for all figures with more than one variable or item displayed. Figure lines should be wide enough to see the line after being copied.

All titles will be centred on a page. The first title line will be the number of the table, figure, or data listing. The second (and if required, third) line will be the description of the table, figure, or data listing. The ICH numbering convention will be used for all TLFs (8).

All tables, figures, and data listings will have the name of the relevant SAS (or Stata) program and a date-time stamp on the bottom of each output. All analysis programs developed for a table, figure, or data listing will be self-contained to facilitate transfer of programs to multiple computing environments. A separate analysis program will be written to produce each table.

### 7.2 Statistical summary conventions

For tables, sample sizes for each treatment group will be presented as totals in the column header (N=xxx), where appropriate. Sample sizes shown with summary statistics are the number (n) of patients with non-missing values.

Summaries for categorical variables will include only categories that patients had a response in. Percentages corresponding to null categories (cells) will be suppressed. All summaries for continuous variables will include: N, mean, and SD. Other summaries (e.g. median, quartiles, 5%, 95% intervals, CV or %CV) will be used as appropriate. All percentages should be rounded and reported to a single decimal place (xx.x%). If percentages are reported as integers, percentages greater than 0% but <1% will be reported as <1%, whereas percentages greater than 99% but <100% will be reported as >99%. A percentage of 100% will be reported as 100%. No value of 0% should be reported. Any computation of percent that results in 0% is to be reported as a blank. Summaries that include p-values will report the p-value to three decimal places with a leading zero (0.001). P-values <0.001 will be reported as <0.001.

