### **1.2 Study synopsis**

The BLOCADE trial is a feasibility study for a large multi-centre, randomised, placebo-controlled trial of the effectiveness of the beta-blocker carvedilol to reduce cardiovascular morbidity and mortality in high-risk patients receiving dialysis. The multi-centre feasibility study had a six week active run-in period during which all participants received carvedilol. After the run-in period participants who tolerated carvedilol were randomised 1:1 to receive carvedilol (experimental intervention) or placebo (control intervention).

The BLOCADE feasibility study began recruiting patients on 16 May 2011 and stopped recruiting on 28 February 2013 due to slow recruitment and lack of funds to continue recruiting participants. In total, 88 participants from 11 sites were consented into the study. Of these, 72 participants from 9 sites entered the run-in phase and 49 participants from 8 sites were randomised. The final end-of-study visit was conducted in June 2014. The central database is expected to be available for analysis by the end of June 2014.

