## 4. STUDY OUTCOME VARIABLES

### 4.1 Primary outcomes

A range of outcome measures were considered primary in order to assess the feasibility of a clinical end-point study with carvedilol as the intervention. These were:

- 1) Tolerability
  - a. The proportion of participants who finish the run-in phase on a twice daily dose of carvedilol of at least 6.25 mg. Participants who enter run-in but do not take any study medication will be counted among those who fail to finish run-in. Those who do not finish the run-in phase as defined above will be classified as a carvedilol-related failure or a failure for other reasons.
  - b. The proportion of participants randomised to carvedilol (placebo) that drop out due to any adverse event attributable to the study product.
  - c. The incidence of major adverse events of symptomatic hypotension and symptomatic bradycardia in participants randomised to carvedilol (placebo).
- 2) Sample size
  - a. The proportion of participants randomised to carvedilol (placebo) that cease study medication for any reason.
  - b. The Proportion of participants randomised to carvedilol (placebo) that are thought to require beta-blocker therapy after randomisation.
  - c. The proportion of participants who withdraw consent to participate in the study after randomisation.
  - d. Overall post-randomisation rate of the proposed composite primary outcome for the clinical end-point study (cardiovascular death, non-fatal myocardial infarction, non-fatal stroke, resuscitated cardiac arrest).
  - e. Overall post-randomisation rate of proposed secondary outcomes for the clinical end-point study (all-cause mortality, the composite primary outcome plus hospital admission for cardiovascular disease, total days in hospital, total days in hospital where cardiovascular disease is the main reason for admission).
- 3) Logistics
  - a. Recruitment rate (number per month)
  - b. The proportion of screened patients eligible for run-in.
  - c. The proportion of participants eligible for run-in who enter run-in.
  - d. The proportion of participants randomised to carvedilol (placebo) that are on a dose of 25 mg twice daily at each titration and follow-up visit.

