### **6.2 Patient characteristics and baseline comparisons**

Demographic and other baseline characteristics will be summarised for participants who entered the run-in phase and by assigned treatment group for those who completed run-in and were randomised to carvedilol or placebo. Categorical variables will be summarised by frequencies and percentages. Percentages will be calculated according to the number of patients for whom data are available. Where values are missing, the denominator, which will be less than the number of patients assigned to the treatment group, will be reported either in the body or a footnote in the summary table. Continuous variables will be summarised by mean and standard deviation as well as quartiles.

The following baseline demographic and clinical characteristics will be presented: gender, age, ethnic origin (Caucasian, ATSI, Maori/Pacific Islander, Asian, Other, Unknown), height, weight, BMI, obesity (BMI <30, BMI ≥30), heart rate, blood pressure (systolic and diastolic), smoking status (never, former, current), primary cause of renal disease (diabetic nephropathy, hypertension/vascular, glomerulonephritis, reflux nephropathy, polycystic kidney disease, other, unknown), failing renal transplant (no, yes), dialysis treatment regimen (APD, CAPD, HD), diabetes mellitus (no, yes), hypertension (no, yes), ischaemic heart disease (no, yes), cardiac failure (no, yes), cerebrovascular disease (no, yes), peripheral arterial disease (no, yes), chronic lung disease (no, yes), quality of life, BNP, and a range of echocardiographic imaging measurements, including left ventricular end diastolic volume, left ventricular end diastolic dimension, left ventricular end systolic volume, left ventricular end systolic dimension, ejection fraction, stroke volume, left atrial size, E/A ratio, E/A duration, E/E' ratio, and global longitudinal strain.

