## 6.5 Analysis of safety outcomes

SAEs and ADRs that occurred during run-in will be summarised as number (percent). Post-randomisation SAE and ADR categories will be cross-tabulated with treatment group and summarised as number (percent).

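### Section 7.2 prints a 0% as a blank and drops empty categories, with no exception for the primary proportions or safety tables; separately, the section 6.3.1 model gives a zero-width interval at zero events

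*SAP*

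**What the plan says.** SAP section 7.2 sets three display rules that act together:

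- On zero percentages: "No value of 0% should be reported. Any computation of percent that results in 0% is to be reported as a blank".
- On empty categories: "Summaries for categorical variables will include only categories that patients had a response in".
- On empty cells: "Percentages corresponding to null categories (cells) will be suppressed".

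The opposite extreme is shown: "A percentage of 100% will be reported as 100" per cent. The section exempts no table.

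The tables it governs include primary results. Section 4.1 defines tolerability outcome 1b as the proportion in each arm who "drop out due to any adverse event attributable to the study product". Outcomes 2a to 2c (stopping study medication, needing a beta-blocker, withdrawing consent) are also proportions, as is 3d (being on the 25 mg dose at each visit). Section 6.3.1 plans drop-out proportions with 95% confidence intervals from an intercept-only binomial model with identity link. Section 6.3.2 applies the same method to the sample-size proportions. Table 9 shows the primary outcomes as number and percent. Under section 6.5, SAE and ADR categories after randomisation are "cross-tabulated with treatment group and summarised as number (percent").

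**The concern.** The study exists to tell planners of a larger trial how well carvedilol is tolerated and what losses to expect. For such a study, zero is a result. No attributable drop-outs on carvedilol would be a leading tolerability finding, and it should be printed as an estimate with its denominator and an interval.

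As written, sections 6.3.1 and 6.3.2 call for an estimate that section 7.2 then says not to print. The rule is also lopsided. The same data would show 100% if coded as participants who stayed on treatment, and a blank if coded as participants who dropped out. In the safety tables, a section 4.4 category with no events in any group is left out, so the table alone does not show that it was looked for and not found.

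The interval is a second, separate weakness. Even if the zero percentage were printed, the model named in section 6.3.1 would attach no uncertainty to it.

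**Working it through.** **The plan's own figure.** Section 3.3 gives 95% limits of 62.5% and 77.5% for 70% tolerability in 150 patients. The standard error is √(0.7 × 0.3 / 150) = 0.0374. With a multiplier of 1.96 the limits are 62.7% and 77.3%; with a multiplier of 2 they are 62.5% and 77.5%. The stated figure is a simple Wald interval. The present point does not depend on it, but the Wald form matters in step 3.

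**1. Arm sizes.** Section 1.2: "49 participants from 8 sites were randomised". Section 3.4 gives 1:1 allocation, so about 24 and 25 per arm. This split is assumed: arm sizes are not stated, and the adaptive allocation could give a slightly different one.

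**2. How often a zero would arise.** The SAP gives no event rates, so a range is assumed, equal in both arms and independent between participants. For true rate q, the chance of no events in an arm of n is (1 − q)^n. Write a = (1 − q)^24 and b = (1 − q)^25. Then both arms are empty with probability ab, exactly one with a + b − 2ab, and at least one with a + b − ab.

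| Assumed rate | Zero in arm of 24 | Zero in arm of 25 | At least one arm zero | Exactly one arm zero (row stays) | Both zero (category left out) |
|---|---|---|---|---|---|
| 1% | 78.6% | 77.8% | 95.2% | 34.1% | 61.1% |
| 2% | 61.6% | 60.3% | 84.8% | 47.6% | 37.2% |
| 5% | 29.2% | 27.7% | 48.8% | 40.7% | 8.1% |
| 10% | 8.0% | 7.2% | 14.6% | 14.0% | 0.6% |

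Outcome 3d could give a zero for another reason. Section 3.1 caps run-in at 6.25 mg twice daily and spreads up-titration over six weeks, and section 6.3.3 lists 6.25, 12.5 and 25 mg. Nobody on 25 mg at an early titration visit is therefore plausible, though this is an inference. Outcome 3d is analysed under section 6.3.3 by a mixed logistic model, so only the blank-percentage issue applies to it here.

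**3. The interval at zero.** For an intercept-only binomial model with identity link, the usual interval is p̂ ± 1.96 × √(p̂(1 − p̂)/n). At p̂ = 0 the square root is 0, so the interval runs from 0 to 0. A numerical fit to 0/25 confirmed this: the limits were zero to eight decimal places.

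**4. What a zero is compatible with.** The exact (Clopper-Pearson) two-sided 95% upper limit for 0/n is 1 − 0.025^(1/n):

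- 0/24: 14.2%
- 0/25: 13.7%
- 0/49 (outcome 2c, which is defined over all randomised participants): 7.3%

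Wilson upper limits are similar: 13.8% for 0/24 and 13.3% for 0/25.

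**5. What is not affected.** Completion of run-in (outcome 1a) cannot be zero, since 49 of the 72 who entered were randomised.

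**The case against.** The strongest reply is that this is table style. Section 7.2 blanks a percentage and says nothing about blanking a count. When one arm is empty and the other is not, the row stays and a 0 can still be printed under a column header giving N. In an arm of 24 or 25 the smallest non-zero percentage is 1/25 = 4.0%, so a reader who knows the convention can decode a blank. This stands. A reader might infer that a zero-event result would be lost from the report altogether; the text supports that only for the percentage and for categories empty in every group.

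A reader might also infer that a blank cannot be told apart from missing data. Section 6.2 does foresee incomplete data ("Percentages will be calculated according to the number of patients for whom data are available"), but it concerns baseline tables and requires the reduced denominator to be shown or footnoted. The ambiguity is real for the percentage cell on its own. It is weaker where the count and N stand beside it.

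Other outputs also help. Symptomatic hypotension and bradycardia are Poisson incidence rates, and the proposed clinical endpoints are counts only, so the percentage rule does not reach either. Deaths, life-threatening events and reasons for withdrawal have their own listings, and section 6.1 plans a flow diagram. The table templates are in a separate document that is not shown; they may already keep fixed rows.

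The missing upper limit cannot be blamed on section 7.2, which suppresses no interval. It comes from the model in section 6.3.1, and printing 0.0% would not cure it.

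Finally, it is tempting to multiply the number of categories in section 4.4 by the chance of a zero and announce a count of blank cells. The documents do not support this. Those categories are overlapping classifications of the same events, and no common event rate is given.

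**Conclusion.** The point holds as a reporting defect with a related interval defect. Section 7.2, followed literally, leaves a zero primary proportion with no printed percentage and removes SAE/ADR categories that are empty in all groups. Section 6.3.1, followed literally, gives such a proportion an interval of no width, where exact upper limits are 14.2% for 0/24 and 13.7% for 0/25. Together they leave a zero drop-out or sample-size result without a usable estimate and interval.

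Zeros are likely enough to plan for: at an assumed 5% rate, about a 49% chance that at least one arm is empty and 8% that both are. These chances rest on the assumed rates, equal rates in both arms, and a 24/25 split. The zero-width interval depends on none of these assumptions, and the upper limits depend only on the arm sizes.

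No design feature or test is affected by the display rule, and non-zero results are displayed as intended. The change should be made, but it is a modest one.

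**What to change.** **In section 7.2**, replace the zero-percent rule and qualify the empty-category rule, for example:

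> Zero counts are reported as 0 (0.0%) with the denominator, and blanks are not used for zeros. In Tables 9, 15 and 16 every prespecified outcome and every SAE and ADR category in section 4.4 is shown, even when empty.

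**In sections 6.3.1 and 6.3.2**, give 95% intervals for the binomial proportions by the Clopper-Pearson or Wilson method, at least whenever the count is zero. Using one method throughout would avoid switching methods according to the result.

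The table templates should be checked against the new wording. The cost is a text edit to the SAP and templates, and slightly longer tables. No new data are needed.

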## 8. TABLES, LISTINGS, AND FIGURES

This section lists the planned tables, listings and figures for the BLOCADE trial. Templates for all planned tables are in a separate document titled BLOCADE SAP Tables, Listings and Figures.

### 8.1 Planned tables

The following are planned summary tables:

- Table 1. Reasons screened patients were not consented into the study
- Table 2. Enrolment by study centre
- Table 3. Stratification variables by treatment group for randomised participants
- Table 4. Withdrawals, protocol deviations and violations during run-in
- Table 5. Withdrawals, protocol deviations and violations by treatment group
- Table 6. Demographic and clinical baseline characteristics for participants who entered run-in, overall and by successful completion of run-in (yes, no) [Table note indicating 16 consented participants did not enter run-in]
- Table 7. Demographic and clinical baseline characteristics by final run-in dose for all participants who entered run-in
- Table 8. Demographic and clinical baseline characteristics by treatment group for randomised participants
- Table 9. Number (percent) for primary outcomes of feasibility, sample size and logistics
- Table 10. Number of proposed primary and secondary outcomes for large clinical endpoint study
- Table 11. Intradialytic hypotensive episodes per dialysis session during run-in
- Table 12. Intradialytic hypotensive episodes per dialysis session overall and by treatment group for randomised participants
- Table 13. Number (percentage) of dialysis sessions during which an intradialytic hypotensive event occurred during run-in
- Table 14. Number (percentage) of dialysis sessions during which an intradialytic hypotensive episode occurred overall and by treatment group for randomised participants
- Table 15. SAEs and ADRs during run-in, overall and by successful completion of run-in (yes, no)
- Table 16. SAEs and ADRs by treatment group for randomised participants

## 8.2 Planned listings

The following are planned data and patient listings:

- Listing 1. Reasons consented participants (n=16) did not enter run-in
- Listing 2. Deaths and life threatening events during run-in
- Listing 3. Post-randomisation deaths and life threatening
- Listing 4. Reasons for patients withdrawing from the study
- Listing 5. Medication compliance problems requiring patient to come off trial

## 8.3 Planned figures

The following are planned summary figures:

- Figure 1. Monthly and cumulative enrolment
- Figure 2. Flowchart of patient progression through the study
- Figure 3. Proportions of participants on each dose of study drug (6.25 mg, 12.5 mg, 25 mg) by treatment group across titration and follow-up visits
- Figure 4. BNP over time (baseline, F6, F12) by treatment group for randomised participants
- Figure 5. EQ5D over time (baseline, F6, F12) by treatment group for randomised participants

